6.1.10.2 Hematology – Blood Transfusion History and Blood Transfusion Record

Blood transfusion history, including red blood cell and/or platelet infusion within 8 weeks prior to HMPL-306 administration, will be recorded during Screening. The type of infusion, number of infusion unit(s), and date of infusion should be recorded. The pre-infusion hemoglobin level and/or platelet count should also be recorded if obtainable (either is acceptable, both are not required).

Blood transfusion record will include red blood cell and/or platelet infusion after the start of study drug administration until end of treatment (EOT) visit. The type of infusion, number of infusion unit(s), and date of infusion should be recorded. The pre-infusion hemoglobin level and/or platelet count should also be recorded if obtainable (either is acceptable, both are not required).

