4.2.8. Transfusion Dependence

Baseline transfusion dependence (TD) is defined as receipt of any transfusions of red blood cells (RBCs) or platelets within 28 days prior to the first dose of stud drug administration. The baseline TD for RBCs is defined as receipt of any transfusions of RBCs within 28 days prior to the first dose of stud drug administration, and baseline TD for platelets is defined as receipt of any transfusions of platelets within 28 days prior to the first dose of stud drug administration.

Post-baseline transfusion independence (TI) is defined as the absence of RBC and platelet transfusions for a prespecified time during treatment period which is defined from the first dose of study drug administration from Cycle 1 in continuous cycle to 30 days after the last dose date or prior to the start of a subsequent anti-tumor therapy (whichever comes first). Two post-baseline TI overall and for its components will be derived based on the pre-specified time.

- Post-baseline TI-4 is defined to have no RBC or platelet transfusion for at least ≥ 4 weeks during treatment period.
- Post-baseline TI-8 is defined to have no RBC or platelet transfusion for at least ≥ 8 weeks during treatment period.
- Post-baseline TI-4 for RBC is defined to have no RBC transfusion for at least ≥ 4 weeks during treatment period.
- Post-baseline TI-8 for RBC is defined to have no RBC transfusion for at least ≥ 8 weeks during treatment period.
- Post-baseline TI-4 for platelet is defined to have no platelet transfusion for at least ≥ 4 weeks during treatment period.
- Post-baseline TI-8 for platelet is defined to have no platelet transfusion for at least ≥ 8 weeks during treatment period.

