5.2.9. Efficacy Analyses

All efficacy analyses will be based on the efficacy analysis set. The response evaluable analysis set will be used to conduct sensitivity analysis for tumor response.

No formal comparison or hypothesis testing is planned for this study. Two-sided 95% confidence intervals (CIs) will be calculated in the applicable summary, unless otherwise specified.

Main efficacy analysis will be repeated by IDH naïve and treated status based on efficacy analysis set.

All efficacy data will be listed.

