5.2.9.4. Baseline Transfusion Dependence and Post-baseline Transfusion Independence

For the baseline TD and post-baseline TI defined in [Section 4.2.8](#), the number and percentage of patients in each endpoint will be summarized descriptively. Clopper-Pearson exact method will be used to construct the two-sided 95% exact CIs.

In addition, shift tables between the baseline TD and post-baseline TI will be provided.

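### Transfusion independence is reported with a CI in all treated patients and judged on the best 4-week stretch, so the TI-4 rate can be high with no drug effect and cannot be read as activity

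*SAP*

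**What the plan says.** SAP 4.2.8 sets two yardsticks. Baseline dependence is "receipt of any transfusions of red blood cells (RBCs) or platelets within 28 days prior to the first dose", so a single transfusion in one fixed window is enough. For independence, "Post-baseline TI-4 is defined to have no RBC or platelet transfusion for at least" 4 weeks and "Post-baseline TI-8 is defined to have no RBC or platelet transfusion for at least" 8 weeks, both within a treatment period that runs from the first Cycle 1 dose "in continuous cycle to 30 days after the last dose date or prior to the start of a subsequent anti-tumor therapy", whichever comes first. No start point is set within that period and baseline dependence is not required. RBC-only and platelet-only forms of both the baseline and post-baseline measures are also defined.

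On the denominator, SAP 5.2.9 says: "All efficacy analyses will be based on the efficacy analysis set". That set is everyone dosed from Cycle 1 Day 1. SAP 5.2.9.4 then says that "the number and percentage of patients in each endpoint will be summarized descriptively", with two-sided exact 95% CIs, and continues: "In addition, shift tables between the baseline TD and post-baseline TI will be provided". Protocol 9.2.7 uses the same 4-week and 8-week criteria. No hypothesis is tested on the endpoint.

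On data collection, Protocol 6.1.10.2 says: "Blood transfusion history, including red blood cell and/or platelet infusion within 8 weeks prior to HMPL-306 administration, will be recorded during Screening". The same section describes the on-study transfusion record as ending at the end-of-treatment visit.

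**The concern.** TI-4 depends on two things: the transfusion dates and how long the patient is followed. Neither the pre-treatment transfusion rate nor baseline dependence enters it. Two consequences follow.

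- Dependence is judged on one window and independence on the best of all overlapping windows. A patient whose transfusion need never changes can be dependent at baseline and independent later, and this becomes more likely the longer the patient is followed.
- The percentage that carries a CI includes patients who needed no transfusions at the start. They can pass with no improvement.

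Post-baseline transfusion independence is a named secondary endpoint under the antitumor-activity objective, in a single-arm study. There is no control group to show what the rate would be without the drug.

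**Working it through.** **Inputs from the documents.** Required gap d = 28 days (TI-4) or 56 days (TI-8); baseline window 28 days; follow-up to last dose + 30 days (SAP 4.2.8). AML patients without at least a partial response are limited to 6 cycles (Protocol 6.2.1.1), so 2, 4 and 6 cycles are used: 56, 112 and 168 days.

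**Assumptions.** Neither document gives a transfusion frequency, a baseline-dependent share or an expected TI rate, so there is no figure to reproduce. I take 1 to 3 transfusion days per 28 days (with some higher rates), unchanged by the drug. Timing is either random (Poisson) or more regular (gamma intervals, shape 4). Death and new therapy are not modelled. TI is read as an unbroken stretch.

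**Step 1: one fixed window.** At 2 per 28 days with random timing, P(no transfusion in 28 days) = e^(−2) = 13.5%. So 86.5% of such patients are dependent at baseline.

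**Step 2: best window.** With rate λ per day, follow-up T and gap d, the probability of at least one gap of length d or more is

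P = Σ (−1)^(j−1) e^(−jλd) [ (λ(T−jd))^j / j! + (λ(T−jd))^(j−1) / (j−1)! ], for j ≥ 1 with jd ≤ T.

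At 2 per 28 days over 4 cycles (λd = 2, T = 4d):
- j = 1: e^(−2)(6 + 1) = 0.947
- j = 2: e^(−4)(8 + 4) = 0.220
- j = 3: e^(−6)(1.333 + 2) = 0.008
- P = 0.947 − 0.220 + 0.008 = 0.736

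The same unchanged patient has a 13.5% chance of being transfusion-free in the baseline window and a 74% chance of meeting TI-4. Under random timing the two periods are independent, so 74% is also the rate among baseline-dependent patients.

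**Step 3: range in baseline-dependent patients, no drug effect, no post-dose tail.** Random timing is from the formula, regular timing from simulation.

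| Transfusion days per 28 days | 1 | 1.5 | 2 | 3 |
|---|---|---|---|---|
| TI-4, random, 2 cycles | 74% | 56% | 41% | 20% |
| TI-4, random, 4 cycles | 96% | 87% | 74% | 44% |
| TI-4, random, 6 cycles | >99% | 96% | 88% | 61% |
| TI-4, regular, 2 cycles | 63% | 29% | 10% | 1% |
| TI-4, regular, 4 cycles | 92% | 60% | 24% | 2% |
| TI-4, regular, 6 cycles | 99% | 77% | 38% | 4% |
| TI-8, random, 4 cycles | 41% | 20% | 9% | 2% |

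At 4 per 28 days over 4 cycles, TI-4 falls to 22% (random) and about 0% (regular).

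**Step 4: effect of the denominator.** Let rates vary between patients (gamma, mean 2 per 28 days, shape 1.5), with random timing over 4 cycles. The non-dependent share is (1 + 2/1.5)^(−1.5) = 28%. Simulated TI-4 is 64% in dependent and 93% in non-dependent patients. The all-patient rate is 0.72 × 64% + 0.28 × 93% = 72%. Across other mixed populations (67% to 96% dependent; 8, 12 or 24 weeks of dosing, tail included), TI-4 is 72% to 99% in non-dependent patients, 13% to 73% in dependent patients and 15% to 82% overall.

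**Step 5: the 30-day tail.** The tail alone is longer than 28 days. At 2 per 28 days, random timing and 12 weeks of dosing:
- Without the tail (T = 84): e^(−2)(4 + 1) − e^(−4)(2 + 2) = 0.677 − 0.073 = 60%.
- With the tail (T = 114): 0.967 − 0.233 + 0.010 = 74%.

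**Step 6: recording period.** If recording stops at an end-of-treatment visit 7 days after the last dose, the remaining 30 − 7 = 23 days are empty by construction. Then 28 − 23 = 5 recorded transfusion-free days complete a TI-4. With weekly transfusions at random times, that stretch alone occurs with probability e^(−5/7) = 49%. By simulation at 12 weeks, TI-4 rises from 23% to 57% (weekly, random) and from 5% to 64% (every 14 days, near-regular). The schedule tables appear to mark the transfusion record at safety follow-up as well; if that governs, the gap closes.

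**The case against.** A reader might infer that the TI-4 rate will be high whatever the drug does. The documents do not support that. It depends on transfusion frequency, regularity and time on treatment, none of which they give. Frequent regular transfusion brings the no-effect rate to about 0%. Time on treatment may also be short: Protocol 2.3.1 puts median survival in refractory AML at about 1.5 months, which favours the 2-cycle rows. This stands, and the claim is limited to *can be high*.

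A reader might also infer that the SAP offers TI-4 alone as proof of activity. It does not. The endpoint is one of several descriptive secondary measures, and no test, dose decision or stopping rule rests on it. Efficacy is shown by dose level, with at least 3 patients planned per level, so intervals will look wide: 3 of 3 gives a lower limit of 0.025^(1/3) = 29%. This limits the consequences.

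The strongest point is that the SAP already plans shift tables, TI-8, component endpoints and full listings. Anyone can take conversion counts from the shift tables and compute an interval. That meets part of the denominator objection. But the named percentage with a CI remains the all-patient one, and the shift tables leave the best-window effect in the dependent row. TI-8 is less affected, yet it is given no priority over TI-4.

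Finally, restricting the denominator does not cure the best-window effect, and a before-and-after rate comparison is itself uncontrolled, open to regression to the mean and informative dropout. Both are true, so the comparison is offered only as optional support.

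**Conclusion.** The point holds in a limited form. From the SAP text alone, the TI percentage and CI cover all treated patients, non-dependent patients can count as successes, and dependence and independence use unequal windows. The all-patient rate therefore cannot be read as antitumor activity.

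The size rests on assumed transfusion rates. Over 4 cycles without the tail, no-effect TI-4 is about 2% to 96% in baseline-dependent patients at 1 to 3 transfusion days per 28 days, and near 0% with more frequent regular transfusion. It is about 93% in non-dependent patients in the mixed population of step 4. Shorter treatment lowers these figures and the post-dose tail raises them. This is worth correcting before the analysis, but it affects the reading of a descriptive secondary endpoint and not the trial's main conclusions.

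**What to change.** In SAP 5.2.9.4:

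1. Report TI-4 and TI-8 rates with Clopper-Pearson CIs among baseline-dependent patients: overall, RBC and platelets. For the RBC and platelet endpoints use the component-specific baseline dependence that SAP 4.2.8 already defines. Show non-dependent patients separately as having maintained independence.
2. State that TI-4 in a single-arm setting is not evidence of activity on its own, and present it next to TI-8.
3. Optionally, tabulate transfusion days per 28 days on treatment against the 8-week pre-dose history, labelled as descriptive and uncontrolled.
4. Reconcile the TI window in SAP 4.2.8 with the recording period in Protocol 6.1.10.2 and the schedule tables, so that unrecorded days are not counted as transfusion-free.

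Items 1 to 3 need SAP wording and one or two tables from data already collected. Item 4 needs a check of what the CRF captured after the end-of-treatment visit. The cost is smaller denominators, possibly very few dependent patients at a given dose level, wider CIs and a less favourable TI rate.

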4.3. Exposure Endpoints

Duration of Exposure

Patients will receive dosing of HMPL-306 PO, QD, in each 28-day cycle. In dose escalation, dose will begin at **cci** mg QD of HMPL-306 in a 28-day continuous dosing treatment cycle. The dose will escalate successively according to the sequence of **cci** mg QD, **cci** mg QD and **cci** mg QD.

In dose expansion, HMPL-306 will be administered PO, QD, in a 28-day continuous dosing treatment cycle at MTD and/or RP2D.

The duration of exposure (months) = [Last non-zero dose date of study drug – first dose non-zero date of study drug (i.e. including single dose during the PK week) + 1] / 30.4375.

The actual duration of exposure (months) = [Cumulative days with non-zero study drug administered, and this includes the single dose during the PK week] / 30.4375.

Dose Intensity and Cumulative Dose

Algorithms for calculating parameters relevant to the dose exposure and intensity are included in [Table 9](#).

Table 9 Algorithms for Calculating Parameters Relevant to the Dose Exposure and Intensity

Parameter	HMPL-306 cc mg [§]
Dosing schedule per protocol	PO, QD, each day in a 28-day treatment cycle
Cumulative dose (mg)	Sum of the doses administered to a patient in the duration of exposure
Dose intensity (mg/day)	Cumulative dose (mg) / (duration of exposure*30.4375)
Relative dose intensity (RDI) (%)	100 * [Dose intensity (mg/day) / cc (mg/day)]
Percentage intended dose (PID) (%)	100 * [(actual duration of exposure) / (duration of exposure)]

[§] Different doses (e.g. ~~cc~~ mg PO QD, ~~cc~~ mg PO QD, etc.) of HMPL-306 may be evaluated. The calculation of relevant parameters will be adjusted accordingly based on the example presented in this table.

PO = *Per os* (oral administration); QD = *Quaque die* (once daily)

In addition, the RDI (%) will be categorized to the groups: < 50%; 50 - < 70%; 70 - < 90%; 90 - < 110%; \geq 110%.

Dose Interruptions, and Dose Reductions

- Dose interruption and dose reductions are all based on the dose administration data, the associated reasons for each of them include categories: (1) Adverse event, (2) DLT, and (3) Other.
- Dose modifications of study drug include dose interruption and dose reduction.

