6.1.1 Study Drug Administration

6.1.1.1 Dose Escalation

A single dose of HMPL-306 will be administered on Day 1 of PK week (Section [6.1.2](#)) for each cohort in the dose escalation part. After PK week, all patients will receive continuous, daily administration of HMPL-306 beginning at C1D1.

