6.1.2 PK Week

The PK week is defined as 7 days prior to C1D1 where a single dose of HMPL-306 will be administered on Day 1 of PK week (Day -7 relative to C1D1). Blood samples and ECG assessments will be collected at intervals as specified in [Appendix 1](#). These samples will be analyzed for plasma concentrations of HMPL-306, 2-HG, and other biological markers as defined by the sponsor. PK week is applicable to every cohort in the dose escalation part only. See [Appendix 1](#) for more details. PK week for a particular dose cohort will be considered optional and not mandatory if PK week data from 5 patients have been collected at the same dose.

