2.2 Study Design

This is a phase 1, open-label, multicenter, single-arm study to evaluate safety, tolerability, PK, PD and preliminary efficacy of HMPL-306 administered orally in treatment of patients with advanced relapsed, refractory, or resistant hematological malignancies that harbor IDH mutations. The study consists of 2 parts: dose escalation part (Part 1) and dose expansion part (Part 2).

The first part of the study is dose escalation, where cohorts of patients will receive ascending oral doses of HMPL-306 to determine MTD and/or the RP2D. The modified toxicity probability interval-2 (mTPI-2) ([Greenberg 2012](#), [Guo 2017](#)) design will be used to perform dose escalation and MTD/RP2D determination. Briefly, the mTPI-2 method uses a Bayesian framework and a hierarchical model to compute the dose escalation based on the interval between the toxicity rate of each dose level and target probability ([Greenberg 2012](#), [Guo 2017](#)). This study is designed targeting a DLT rate of 20% with an equivalence interval of 15% to 25%.

Seven days prior to initiating daily administration of HMPL-306 from Cycle 1 Day 1 (C1D1), patients enrolled in each cohort during dose escalation will be administered a single oral dose of HMPL-306 on Day -7 relative to C1D1 (Day 1 of PK week). Serial blood samples will be collected from Days 1 to 7 of the PK week for analysis of plasma concentrations of HMPL-306 and 2-HG.

A cycle of study treatment is defined as 28 days of continuous daily dosing. After the PK week, dose escalation will start at **[REDACTED]** mg QD orally (PO) for Cohort 1 and then escalate in the sequence of **[REDACTED]** mg QD, and **[REDACTED]** mg QD.

Safety monitoring and evaluation of dose escalation will be carried out by the Safety Review Committee (SRC), which is comprised of the sponsor and investigators.

[figure not shown]
In the dose-expansion part, 1 cohort of patients will receive HMPL-306 at MTD and/or RP2D to evaluate further the safety, tolerability, PK, PD, and preliminary efficacy in approximately 10 patients with advanced relapsed, refractory, or resistant hematological malignancies with IDH mutations. Patients enrolled in the dose expansion part must not have standard therapeutic options available (including IDH inhibitors where approved) and must have the following:

- Relapsed AML unsuitable for intensive chemotherapy or venetoclax-based regimen or target agents;

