5. ANALYSIS METHODS

5.1. General Principles

5.1.1. General Methodology

In general, all efficacy, safety and PK variables will be summarized using descriptive statistics and graphs as appropriate. Continuous variables will be summarized by descriptive statistics (observed number (n), mean, standard deviation, minimum, 25% percentile (Q1), median, 75% percentile (Q3), and maximum). Categorical variables will be summarized in frequency tables (frequencies and percentages).

Time to event variable will be analyzed using Kaplan-Meier method and summarized with median, 25% and 75% percentiles with their corresponding 95% confidence intervals (CI) which are calculated from a log-log transformation based on the method by [Brookmeyer and Crowley \(1982\)](#). Individual data will be presented in patient listings.

Analyses will be implemented using SAS Enterprise® Version 8.3 or higher (SAS Institute, Cary, North Carolina, USA). The International Conference on Harmonization (ICH) numbering convention, i.e. ICH-E3, will be used for all tables and listings.

Unless otherwise specified, analyses will be summarized:

- Efficacy analysis: by dose level for escalation stage (part 1) and by disease type for dose expansion (part 2).
- Analysis besides efficacy: by dose level and total for escalation stage (part 1) and by disease type and total for dose expansion (part 2).

In addition, main efficacy analysis will be repeated by IDH naïve/treated status (as defined in [Section 5.2.4](#)) and dose level for escalation stage (part 1) and by disease type for dose expansion (part 2).

Analysis will be conducted on the basis of first dose of study drug that a patient received. Hence, all summary tables, listings, and figures (TLFs) will be presented by treatment groups as defined in [Table 13](#).

Table 13 Group Display in TLFs

Part of the study	Treatment Group	Treatment Description in Data Display
Part 1 - Dose Escalation	1	Cohort 1- XX mg
	2	Cohort 2- XX mg
	3	Cohort 3- XX mg
	4	Cohort 4- XX mg
	5	Cohort 5- XX mg
	6	Cohort 6- XX mg
	7	Cohort 7- XX mg
	8	Cohort 8- XX mg
Part 2 - Dose Expansion at HMPL-306 XX mg*	1	Cohort A: AML

*As only one patient at HMPL-306 [REDACTED] mg was enrolled in Part 2 Dose expansion Cohort A, this patient will be combined into Part 1 Dose escalation Cohort 8 [REDACTED] mg in all the summary tables and figures.

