5.2.10. Exposure of Study Treatment

Exposure of study treatment described in [Section 4.3](#) (duration of exposure, actual duration of exposure, cumulative dose, dose intensity, relative dose intensity, relative dose intensity category, and percentage intended dose for study drug) will be summarized on safety analysis set.

The following summary for dose modification will also be summarized.

- Number of patients with any dose modification (including both drug interruption and dose reduction)
- Number of patients with any drug interrupted (number of patients experienced drug interruption and reasons for drug interruption)
- Number of patients with any dose reduced (number of patients with any dose reduction and reasons for dose reduction)

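### SAP Table 9 counts six PK-week days with no planned dose in RDI and percentage intended dose, so a fully compliant Part 1 patient shows 82.9% after one cycle

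*SAP*

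**What the plan says.** SAP section 2.2 states that each patient in dose escalation "will be administered a single oral dose of HMPL-306 on Day -7 relative to C1D1". Protocol section 6.1.1.1 continues: "After PK week, all patients will receive continuous, daily administration of HMPL-306 beginning at C1D1". Protocol Appendix 1 agrees, marking drug intake on PK-week Day 1 and next on C1D1. Protocol section 7.1 sets the PK-week dose at the cohort's own dose level.

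SAP section 4.3 measures the duration of exposure from the last non-zero dose back to the "first dose non-zero date of study drug (i.e. including single dose during the PK week) + 1] / 30.4375". Actual duration of exposure counts days with a non-zero dose, and the PK-week dose adds one such day. Table 9 then defines:

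- dose intensity as "Cumulative dose (mg) / (duration of exposure*30.4375") in mg/day;
- RDI as 100 times dose intensity over the assigned daily dose;
- PID as "100 * [(actual duration of exposure) / (duration of exposure")].

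RDI is also grouped: below 50%, 50 to <70%, 70 to <90%, 90 to <110%, and 110% or more. SAP section 5.2.10 lists the outputs, ending with "relative dose intensity category, and percentage intended dose for study drug) will be summarized on safety analysis set".

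The Table 9 footnote adapts the formulas to other dose levels only. SAP section 7 does not mention the gap.

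**The concern.** RDI and PID both imply a comparison with what was planned. A patient who takes every planned dose should score 100%. With a PK week followed by continuous dosing this cannot happen, because the denominator holds six days on which the protocol plans no drug and treats each as a dosing day. The tables would then suggest under-delivery where there was none, most strongly for patients treated briefly.

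The ordering can also reverse. A patient who receives the PK-week dose and never starts daily dosing scores 100%, above one who completes a perfect cycle.

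Patients with and without a PK week are not comparable. Part 2 has no PK week, yet under the Table 13 footnote the one Part 2 patient is pooled: "this patient will be combined into Part 1 Dose escalation Cohort 8". In Part 1, Protocol section 6.1.2 says the PK week "will be considered optional and not mandatory if PK week data from 5 patients have been collected at the same dose", so some Part 1 patients may also lack one, although the documents do not show that any did. Cohorts can be as small as three patients, so one patient in the wrong RDI group can be a third of a column.

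**Working it through.** The documents state no RDI or PID value, so there is no figure to reproduce. The formulas were applied to the planned schedule.

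**Inputs**
- PK-week dose on Day -7 relative to C1D1, so C1D1 = first dose date + 7 (SAP 2.2; Protocol 6.1.2).
- Daily dosing from C1D1 (Protocol 6.1.1.1).
- PK-week dose equal to the cohort dose D (Protocol 7.1).
- T = days of continuous dosing from C1D1 to last dose, with every dose taken and none reduced.

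**Formulas**
- Last dose date = C1D1 + T - 1.
- Duration of exposure in days = last - first + 1 = (7 + T - 1) + 1 = T + 7. The factor 30.4375 cancels.
- Doses taken = days dosed = T + 1.
- RDI = [D(T+1)/(T+7)]/D = (T+1)/(T+7). The redacted dose D cancels.
- PID = (T+1)/(T+7).

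**Results, full compliance with a PK week (T ≥ 1)**

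| T (days) | Doses / span | RDI = PID | SAP RDI group |
|---|---|---|---|
| 4 | 5/11 | 45.5% | <50% |
| 5 | 6/12 | 50.0% | 50 to <70% |
| 12 | 13/19 | 68.4% | 50 to <70% |
| 13 | 14/20 | 70.0% | 70 to <90% |
| 14 | 15/21 | 71.4% | 70 to <90% |
| 28 | 29/35 | 82.9% | 70 to <90% |
| 42 | 43/49 | 87.8% | 70 to <90% |
| 52 | 53/59 | 89.8% | 70 to <90% |
| 53 | 54/60 | 90.0% | 90 to <110% |
| 56 | 57/63 | 90.5% | 90 to <110% |
| 84 | 85/91 | 93.4% | 90 to <110% |
| 168 | 169/175 | 96.6% | 90 to <110% |

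The cut-points follow directly. (T+1)/(T+7) ≥ 0.9 requires 0.1T ≥ 5.3, so T ≥ 53. The 70% limit requires 0.3T ≥ 3.9, so T ≥ 13. The 50% limit requires 0.5T ≥ 2.5, so T ≥ 5.

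**Comparison cases**
- PK-week dose only: 1 dose in a 1-day span, 1/1 = 100%.
- No PK week, 28 of 28 doses: 100%.
- No PK week, 5 of 28 doses missed: 23/28 = 82.1%, close to the 82.9% of a fully compliant patient with a PK week.
- PK week, 5 of the 28 daily doses missed, last dose on Day 28: 24/35 = 68.6%, although 24 of 29 planned doses (82.8%) were taken.

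**The case against.** The strongest reply is that this is a definition, not a miscalculation. Protocol section 9.2.4 asks for dose intensity and RDI without defining them, so Table 9 contradicts no stated figure. The SAP includes the PK-week dose on purpose, in line with its safety reference start date. RDI as written is delivered mg/day over a declared span relative to the daily dose, not a count of missed doses. That argument supports duration of exposure and mg/day dose intensity, which are valid descriptions. It does not support a full daily dose as the comparator on days with no planned dose, and it fails outright for PID, whose name claims a comparison with intended dosing.

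On weight, the objection largely stands. No decision rule uses RDI or PID, no hypothesis is tested, and dose interruptions and reductions are tabulated separately with reasons. The offset is a fixed six days that fades with longer treatment. The lowest RDI groups are reached only by patients who stop within 12 days of C1D1, and the documents give no treatment durations. Part 1 patients without a PK week may not exist: Protocol section 7.2.2.2 calls the PK week mandatory, and only the one pooled Part 2 patient is documented.

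Two practical points also stand. If RDI is rebased while mg/day keeps the full span, the two lines no longer reconcile without a note. And counting planned days from the actual C1D1 hides any delay between the PK-week dose and C1D1.

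**Conclusion.** The concern holds. For a Part 1 patient with a PK week who goes on to daily dosing, RDI and PID as written cannot reach 100% under full compliance. The shortfall is 6/(T+7): 17.1 percentage points at 28 days, 9.5 at 56 and 3.4 at 168. Such a patient falls below the 90 to <110% group for every T from 1 to 52.

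This assumes C1D1 exactly seven days after the PK-week dose, as the protocol defines it; a later C1D1 lowers the values further. How many patients change RDI group is unknown. The consequence is limited to the descriptive exposure and tolerability tables. DLT evaluability rests on C1D1 to C1D28 and is untouched, as are the MTD and RP2D rules. The change should be made, but it does not threaten the trial's conclusions.

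**What to change.** Replace two rows of SAP Table 9. Let P = 1 if a PK-week dose was given and 0 otherwise, and let T be the days from C1D1 to last dose (0 if daily dosing never started). Planned dosing days are P + T.

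- RDI = 100 × cumulative dose / [assigned daily dose × (P + T)].
- PID = 100 × days dosed / (P + T).

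Full compliance then gives 29/29 = 100% with a PK week at T = 28, 28/28 = 100% without one, and 1/1 = 100% for the PK-week dose only.

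Keep duration of exposure including the PK week, and mg/day dose intensity over that span, as descriptive lines. Add a footnote saying that mg/day uses the full calendar span, so it will not reconcile with RDI, and that a delayed C1D1 is not reflected in RDI or PID.

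Alternatively, compute both measures from C1D1 and show patients dosed only in the PK week as not applicable. The PK-week dose must then leave the numerators too; moving the denominator alone would give 29/28 = 103.6%.

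The cost is two formula rows, one definition, a footnote and the matching programming. No new data are needed.
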